### 7.3.3 Visit 2 (Day 15 ±2; End of Treatment Period)

During this visit the following data will be collected:

- Vital signs (including pulse, respirations rate, body temperature, systolic and diastolic blood pressure, SpO2)
- Assess measures of clinical support
  - Hospitalized
  - Oxygen requirement
  - Non-invasive mechanical ventilation (via mask)

- Mechanical ventilator requirement (via endotracheal tube or tracheostomy tube)
- ECMO requirement
- Ordinal Scale Assessment
  1. Not hospitalized, no limitations on activities
  2. Not hospitalized, limitation on activities
  3. Hospitalized, not requiring supplemental oxygen
  4. Hospitalized, requiring supplemental oxygen
  5. Hospitalized, on non-invasive ventilation or high flow oxygen devices
  6. Hospitalized, on invasive mechanical ventilation or ECMO
  7. Death
- NEW Score
- SARS-CoV-2 RNA status testing
- Cytokine Markers
- Safety laboratory Testing
- PaO2 and PaO2/FiO2 ratio
- VAS (if not performed on Day 14; if possible)
- Extent of Dyspnea (if not performed on Day 14; if possible)
- Adverse Events recorded
- Concomitant medications

It is understood that restrictions on the return of study patients to the clinical site may be in place after their discharge from hospital. If not possible for the patient to return, the site may use remote methods (for example Telehealth, remote or nurse for hire, remote laboratories) to obtain the visit specific measurements/samples for both Visits 2 (Day 15; End of Treatment) and 3 (Day 29; Safety Follow Up Visit).

#### **7.3.4 Visit 3 (Day 29 ±2; Safety Follow Up Visit)**

For all continuing patients, a Safety Follow-up Visit will be scheduled on Day 29 (Week 4). For patients that have discontinued from the study, they will be invited to attend a Safety Follow up visit 7 days after their last dose of IP and following the same schedule of events as Visit 3.

The following data will be collected:

- Vital signs (including pulse, respirations rate, body temperature, systolic and diastolic blood pressure, SpO2)
- Assess measures of clinical support
  - Hospitalized
  - Oxygen requirement
  - Non-invasive mechanical ventilation (via mask)
  - Mechanical ventilator requirement (via endotracheal tube or tracheostomy tube)
  - ECMO requirement
  - Ordinal Scale Assessment
    8. Not hospitalized, no limitations on activities
    9. Not hospitalized, limitation on activities
    10. Hospitalized, not requiring supplemental oxygen
    11. Hospitalized, requiring supplemental oxygen
    12. Hospitalized, on non-invasive ventilation or high flow oxygen devices
    13. Hospitalized, on invasive mechanical ventilation or ECMO

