#### 5.4.2 Discontinuation of Study Drug

A patient in this clinical study may discontinue study drug for any of the following reasons:

- An adverse event which, in the opinion of the Investigator necessitates withdrawal of study drug
- A patient's substantial non-compliance (e.g. visits non-compliance)
- The Investigator's opinion that continuing the patient in the trial is not appropriate. The Investigator may withdraw a patient at any time if it is considered to be in the patient's best interest.
- Patient requests to discontinue study drug
- Patients who suffer vasodilative shock. However, physicians can use rescue therapy such as vasopressin to restore blood pressure and allow patients to continue in the study, at the discretion of the attending physician.
- Patients whose ALT/AST rise to >5x upper limit of normal or Child Pugh score of 10-15.
- Patients who experience a cerebral hemorrhage or cerebral infarction

Patients discontinued from study treatment should remain in the study and complete all remaining study assessments. If not possible, at a minimum, they should be invited to a Safety Follow-up Visit 7 days after the last dose of IP as soon as possible after a decision of discontinuation has been taken. At these visits, the Investigator will obtain all the required details and document the date of the premature termination and the main reason in the e-CRF. If the reason for study drug discontinuation is an adverse event, the specific event will be recorded in the e-CRF.

NOTE: patients that progress to mechanical ventilation during the study may remain on study drug and should not be withdrawn.

Definition of Dose Limiting Toxicity:

The occurrence of any of the following toxicities from the initial dose of Ifenprodil administration (in combination with Standard of Care (SOC)) which results in:

- a. The necessity to delay ifenprodil administration in the participant, OR
- b. To reduce the dose of ifenprodil administered, either for the participant, or for subsequent participants,

will be considered a DLT, if judged by the investigator to have a reasonable possibility of being related to the ifenprodil administration.

Severity is graded according to the NCI Common Terminology Criteria for Adverse Events (CTCAE), Version 5.0 equivalents of mild, moderate or severe:

1. Grade 3 or higher toxicity, except elevations in gamma-glutamyltransferase (GGT)

2. Grade  $\geq 3$  AST/ALT elevation

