#### 5.4.3 Withdrawal of Patients from the Study

The Investigator also has the right to withdraw patients from the study post initial dosing. Whenever possible the patient should be followed for all assessments per protocol. Patients will be withdrawn in the following circumstances:

- Patients withdraws consent or requests discontinuation from the study for any reason
- Death of the patient
- Termination of the study
- Loss to follow-up (every effort must be made to contact the patient; phone calls on three separate days must be made, and a certified letter must be sent to the patient's most recent address)

Any withdrawal must be fully documented in the e-CRF and source documents, registered in the e-CRF as discontinued, and followed by the Investigator/Investigative Staff. Patients who withdraw from the study or are lost to follow-up after signing the informed consent form and randomization will not be replaced.

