### 6.2 Treatment Administration and Schedule

Tablet/s (20 mg TID arm = 1 tablet; 40 mg TID arm = 2 tablets) will be taken by mouth TID after food (if possible) in the in the morning (AM, upon rising), in the afternoon (PM, 6-10 hours following first dose), and evening (PM, 6-10 hours before the next day's anticipated first dose). Best efforts should be made to keep the three doses approximately 8 hours apart. The length of dosing for the study is up to 2 weeks (either to hospital discharge, or Day 14, whichever comes first).

The first dose of study medication will be taken on day 1 at the first visit, following randomization.

In cases where the patient is unable to swallow tablets the use of a nasogastric/stomach tube is permitted. Crushing and administration of tablets should follow local practices/SOPs.

Study drug administration should continue until the end of Day 14, or hospital discharge, whichever comes first.

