### **8.5 Pregnancy**

All pregnancies or suspected pregnancies occurring in either a female patient or partner of a male patient must be reported immediately. The IP should be discontinued, and the patient withdrawn from the trial.

The Investigator will follow the female patient until completion of the pregnancy and collect the outcome of the pregnancy (either normal or abnormal outcome).

If the outcome of the pregnancy was abnormal, the Investigator should report the abnormal outcome as an AE. If the abnormal outcome meets any of the serious criteria, it must be reported as an SAE within 24 hours of the Investigator's knowledge of the event. All neonatal deaths that occur within 28 days of birth should be reported, without regard to causality, as SAEs. In addition, any infant death after 28 days that the Investigator suspects is related to the in-utero exposure to the IP should also be reported within 24 hours of the Investigator's knowledge of the event.

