3.1 General Considerations

All data collected on the electronic case report form (eCRF) will be presented in the data listings and will be listed and sorted by treatment arm, participant number and visit, where applicable. All descriptive summaries will be presented by treatment group and scheduled visit/time point (where applicable).

Unless otherwise stated, the following methods will be applied:

- **Continuous variables:** Descriptive statistics will include the number of non-missing values (n), arithmetic mean, standard deviation (SD), median, minimum and maximum values.

The minimum and maximum values will be displayed to the same decimal precision as the source data, the arithmetic mean, SD and median values and other derived values will be displayed to one more decimal than the source data for the specific variable.

95% Confidence Intervals (CIs), mean differences (among treatments and from baseline) and adjusted means values will be displayed to one more decimal than the source data for a specific variable. P-values will be displayed to 3 decimal places.

The appropriate precision for derived variables will be determined based on the precision of the data on which the derivations are based, and statistics will be presented in accordance with the aforementioned rules.

- **Categorical variables:** Descriptive statistics will include counts and percentages per category. The denominator in all percentage calculations will be the number of participants in the relevant analysis population with non-missing data, unless specifically stated otherwise. Percentages will be displayed to one decimal place. Proportions will be displayed to 3 decimal places.

95% Confidence Intervals (CIs), difference in proportions, odds ratio's and other categorical parameters will be displayed to one decimal place for percentages. Proportions will be displayed to 3 decimal places. P-values will be displayed to 3 decimal places.

- **Repeat/unscheduled assessments:** Only values collected at scheduled study visits/time points will be presented in summary tables. If a repeat assessment was performed, the result from the original assessment will be presented as the result at the specific visit/time point. All collected data will be included in the data listings.
- **Assessment windows:** All assessments will be included in the data listings and no visit windows will be applied to exclude assessments that were performed outside of the protocol specified procedure windows.

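### The only dated minimum visit for early leavers is timed from the last ifenprodil dose, so it gives no date for SOC-only patients and does not target Day 15 or Day 29

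*Protocol*

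**What the plan says.** The protocol has a first request and a fallback.

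- **First request.** Section 5.4.2 states: "Patients discontinued from study treatment should remain in the study and complete all remaining study assessments". Section 5.4.3, on withdrawal from the study, adds for every arm: "Whenever possible the patient should be followed for all assessments per protocol". Section 5.4.1 asks sites to encourage patients to stay for their planned outcome assessment, and bars new eCRF data once consent is withdrawn.
- **Fallback.** Where the remaining assessments are not possible, 5.4.2 says of patients who stopped drug that, "at a minimum, they should be invited to a Safety Follow-up Visit 7 days after the last dose of IP". Section 7.3.4 applies a visit at the same interval to patients who have discontinued from the study, as a "Safety Follow up visit 7 days after their last dose of IP and following the same schedule of events as Visit 3".

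Dosing starts on Day 1 (6.2), and "Study drug administration should continue until the end of Day 14, or hospital discharge, whichever comes first". The control arm receives SOC only (4.1).

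The primary endpoint is WHO-7 status at Day 15 (Protocol 3.2, SAP 2.3.1). SAP 3.3 imputes nothing unless stated otherwise, and SAP 11.1 carries death forward. SAP 3.1 limits summary tables to scheduled visits and time points, and says that "no visit windows will be applied to exclude assessments that were performed outside of the protocol specified procedure windows". Neither document says how the early-leaver visit is labelled or mapped.

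On pregnancy in a patient or a male patient's partner, Protocol 8.5 says: "The IP should be discontinued, and the patient withdrawn from the trial".

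**The concern.** A fallback matters when the main request has failed, and here it is defined by exposure to the test drug. A leaver in either ifenprodil arm has a dated visit to be invited to. A leaver in the SOC arm has only the undated wording of 5.4.3. In an open-label add-on trial, leaving may itself depend on the arm, so a minimum that also differs by arm is best avoided.

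The visit is also aimed at neither efficacy time point. A living patient who leaves before Day 15 has no primary outcome unless someone obtains the score, and the minimum does not ask for it. The visit does use Visit 3 procedures, so it can produce WHO-7, NEWS, PaO2 and cough VAS values from the acute phase with no rule for where they go.

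**Working it through.** **Inputs.** Last dose on Day 1 to 14 (Protocol 6.2). Visit 7 days later (5.4.2, 7.3.4). Visit 2 window is Day 15±2, i.e. Days 13 to 17 (7.3.3). Visit 3 window is Day 29±2, i.e. Days 27 to 31 (7.3.4). Allocation 1:1:1 (4.1). Drop-out 10%, 168 enrolled (10.3).

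**1. The plan's own figure.** 50 / (1 − 0.10) = 55.6, rounded up to 56 per arm; 3 × 56 = 168. This reproduces the stated enrolment.

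**2. Where the visit falls.** Visit day = last-dose day + 7.

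| Last dose | Visit | Against Days 13–17 | Against Days 27–31 |
|---|---|---|---|
| Days 1–5 | Days 8–12 | before | before |
| Days 6–10 | Days 13–17 | inside | before |
| Days 11–14 | Days 18–21 | after | before |

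The visit is inside the Day 15 window for 5 of 14 possible last-dose days (36%) and outside it for 9 of 14 (64%). It falls on Day 15 itself only after a last dose on Day 8. To fall within Days 27 to 31, the last dose would have to be on Days 20 to 24, after dosing has ended. The visit is therefore always 29 − 21 = 8 to 29 − 8 = 21 days before Day 29. A last dose on Day 3, for example, gives a visit on Day 10, 19 days early.

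**3. Sensitivity to the unknown distribution of last-dose days.** The documents give none, so these are assumptions:

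- All days equally likely: 64% miss the Day 15 window.
- Constant daily stopping rate h, with weights (1 − h)^(d − 1) on last-dose day d: 65% miss at h = 2%, 66% at 5%, 69% at 10% and 77% at 20%.
- Any pattern in which earlier stopping is at least as likely as later stopping: at least 50% miss. The minimum is reached when last doses are spread evenly over Days 1 to 10, where 5 of 10 hit.
- Extremes: 0% miss if every last dose is on Days 6 to 10, and 100% if none is.

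**4. SOC arm.** There is no last-dose day, so the formula has no input.

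**5. How many patients.** 0.10 × 168 = 16.8 leavers. With equal drop-out by arm, 16.8 × 2/3 = 11.2 are on ifenprodil and 16.8 / 3 = 5.6 on SOC. This is a ceiling: it includes consent withdrawals (no new data in any arm), deaths, losses to follow-up, and patients who leave after Visit 2 with Day 15 already recorded.

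**6. What happens to the data.** If the visit is entered as Visit 3, no SAP rule keeps it out of the Day 29 summaries and comparisons (SAP 11.4.2, 11.5.2, 11.7.1, 11.11). If it is entered as unscheduled, SAP 3.1 removes it from the summary tables. The documents do not choose between the two.

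**7. Passages that do not agree.** Section 5.4.2 attaches the 7-day visit to patients who stopped drug, whereas 7.3.4 attaches it to patients who left the study. Section 8.5 ends trial participation on pregnancy, while 5.4.2 keeps patients who stop drug in the study and the withdrawal list in 5.4.3 does not mention pregnancy.

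**The case against.** The strongest reply is that the 7-day visit is a safety visit. Its timing matches SAE reporting, which runs to 7 days after the last dose (Protocol 8.6.2), and SOC patients have no study drug to stop. Follow-up of outcomes is handled elsewhere: full follow-up in 5.4.2 and 5.4.3, remote Visits 2 and 3 in 7.3.3, a Day 60 phone call in 7.3.5, and calls on three days plus a certified letter before a patient counts as lost. Much of this stands, and it is why the 7-day visit should be kept. It also rules out two stronger readings.

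- A reader might infer that SOC leavers get no follow-up at all. The documents do not support that, because 5.4.3 covers every arm. What SOC leavers lack is a dated minimum.
- A reader might infer that Day 29 data in the ifenprodil arms will be contaminated. That is a possibility only. Section 7.3.4 fixes the procedures, not the label; the SAP sentence on windows opens by speaking of listings, and summary tables take scheduled visits only. The outcome turns on an eCRF label that is not shown.

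Section 5.4.2 also speaks of acting as soon as possible after the decision to discontinue. That could be read as a second anchor, but it concerns stopping study drug and so does not reach SOC patients.

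Finally, the SAP covers Phase 2b only and calls it exploratory, and a placebo arm in Phase 3 would give controls a dosing date. That limits the stakes. It would remove the missing SOC date in Phase 3, but not the mismatch with Days 15 and 29.

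**Conclusion.** The point holds as a gap in the stated minimum, not as a failure of follow-up. The minimum has no date for SOC-only patients and does not ask for the primary outcome. In the ifenprodil arms it falls on Days 8 to 21, inside the Day 15 window for 5 of 14 possible last-dose days and inside the Day 29 window for none. That it more often misses Day 15 is a count of days, or rests on an assumed stopping pattern; the documents give no observed distribution.

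At most about 17 of 168 patients could be affected, about 11 on ifenprodil and 6 on SOC if drop-out is equal by arm. The true number is lower once the exclusions above are made. With about 50 evaluable patients per arm, a few avoidable missing Day 15 scores are still worth preventing. The change is advisable and cheap, not essential to the trial's validity. The pregnancy conflict is secondary and calls only for reconciliation.

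**What to change.** - In Protocol 5.4.2 and 7.3.4, set one minimum for all three arms, counted from randomisation. For any patient who has not refused further data collection, obtain WHO-7 at Day 15 and Day 29 and vital status at Day 60, by phone, remote visit or hospital record.
- Keep the 7-day post-dose visit as an additional safety visit with its own eCRF label, for example Early termination.
- State in SAP 3.1 that this visit is not mapped to Visit 3 or Day 29.
- Reconcile 5.4.2 with 7.3.4 on which patients the 7-day visit applies to, and 8.5 with 5.4.2 and 5.4.3 on whether stopping drug ends study participation.

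The cost is a protocol wording change, one eCRF visit label and one SAP sentence, plus a phone call or chart check for a few patients.

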#### 14. Death

##### ○ NEW Score

- SARS-CoV-2 RNA status testing (if still positive on Day 15)
- Safety laboratory Testing
- PaO2 and PaO2/FiO2 ratio
- VAS (if possible)
- Extent of Dyspnea (if possible)
- Adverse Events recorded
- Concomitant medications

#### **7.3.5 Visit 4 (Day 60±2; Vital Status Follow Up Visit)**

At the Safety Follow-up Visit, the following data will be collected:

- Vital Status (alive, deceased)
- Adverse Events recorded

Note: This visit may be conducted via phone call.

### **7.4 Assessments**

#### **7.4.1 Vital Signs**

Vital signs will be measured as indicated in [Section 7.3](#) and [Table 3](#) and will include blood pressure (measured after the patient has been in a seated position, if possible, for ≥3 minutes of rest), pulse, respiration rate, body temperature, SpO2, and weight and height (screening visit only). Standard of care measurements can be used if they fall within the protocol specific windows.

The Investigator should evaluate the clinical significance of the results. Clinically significant abnormal findings will be reported as adverse events.

#### **7.4.2 Safety Laboratory Parameters**

Samples for laboratory analysis in local laboratories will be collected during the study at time point specified in the schedule of events (See [Table 3](#) and [Section 7.3](#)). All safety laboratory tests will be analyzed at the local laboratory, unless specified in the protocol. Standard of care measurements can be used if they fall within the protocol specific windows.

The Investigator will review the laboratory results and evaluate and document whether the results are normal or abnormal and whether abnormal results are non-clinically significant or clinically significant. Pre-existing clinically significant conditions diagnosed as a result of the screening procedures must be recorded as medical history. If any clinically significant abnormal findings are discovered after informed consent or any pre-existing conditions worsen during the trial, these must be recorded as adverse events. The laboratory report will be signed and dated by the Investigator.

##### **7.4.2.1 Hematology**

Hemoglobin, hematocrit, white blood cell counts, including differential, platelet count, red blood cell count, myoglobin

#### 7.4.2.2 Chemistry

Glucose, blood urea nitrogen (BUN), serum creatinine, sodium, potassium, chloride, bicarbonate, ALT, AST, GGT, alkaline phosphatase, total bilirubin, calcium, phosphorus, albumin, total protein, uric acid

#### 7.4.2.3 Coagulation

APTT, PT, INR, D-dimer.

#### 7.4.2.4 Urinalysis

Specific gravity, hydrogen ion concentration (pH), protein, glucose, bilirubin, ketone, urobilinogen, blood, leukocytes, casts, bacteria.

#### 7.4.3 Cytokine Markers

The following cytokines should be collected if available at local laboratory: IFN- $\gamma$ , GM-CSF, IL-6, IL-12, TNF- $\alpha$

Cytokine markers to be collected at Baseline, Day 5, Day 15.

#### 7.4.4 Clinical support status

Patients will be assessed for their measures of clinical support, including:

- Hospitalized
- Oxygen requirement
- Non-invasive mechanical ventilation (via mask)
- Mechanical ventilator requirement (via endotracheal tube or tracheostomy tube)
- ECMO requirement
- Ordinal Scale Assessment
  - The ordinal scale is an assessment of the clinical status at the first assessment of a given study day. Each day, the worse score for the previous day will be recorded. i.e. on Day 3, Day 2 score is obtained and recorded as Day 2.
  - For the purposes of baseline the worse score from the previous day (Day -1) will be used
  - The scale is as follows:
    1. Not hospitalized, no limitations on activities
    2. Not hospitalized, limitation on activities
    3. Hospitalized, not requiring supplemental oxygen
    4. Hospitalized, requiring supplemental oxygen
    5. Hospitalized, on non-invasive ventilation or high flow oxygen devices
    6. Hospitalized, on invasive mechanical ventilation or ECMO
    7. Death

#### 7.4.5 National Early Warning Score (NEWS)

The NEW score has demonstrated an ability to discriminate patients at risk of poor outcomes ([WHO R&D Blueprint Master Protocol](#); [Royal College of Physicians 2012](#) and [2017](#)). This score is based on 7 clinical parameters. The NEW Score is being used as an efficacy measure.

This should be evaluated at the first assessment of a given study day. These parameters can be obtained from the hospital chart using the last measurement prior to the time of assessment. This is recorded for the day obtained. i.e. on Day 3, Day 3 score is obtained and recorded as Day 3.

A copy of the Table for determining NEW Score can be found in [Appendix 16.1](#).

#### **7.4.6 Demography**

Demographic data will be collected at the Screening Visit, including gender, date of birth, race, and ethnic origin (to the extent allowed by local regulations).

